- Does participation in the TRAC intervention lead to improvements in medication adherence?

- Does participation in the TRAC intervention impact other clinical HIV outcomes, including CD4 count and viral load?

3. Study Objectives

The aim of the study is to conduct a pilot randomized controlled trial of the TRAC intervention among PLWHA:

- Two-month, randomized-controlled waitlist trial with 2-month follow-up ($N=50$)
- Feasibility evaluation, focusing on recruitment, engagement, and adherence
- Evaluation of effects on overall alcohol consumption, HAART adherence, and clinical outcomes

4. Study Design

Description of relevance to the VA

HIV occurs among veterans at a higher rate than among those in the general population. Moreover, many veterans struggle with alcohol use disorders, which can impact their health and overall quality of life. The TRAC intervention, which aims to reduce alcohol use among people living with HIV/AIDS, thus meets two important needs among the VA patient population.

Study Population and patient selection

Subject Inclusion Criteria: To be eligible to participate in the intervention, patients must be 1) HIV-positive, 2) 18 years and older, 3) an at-risk drinker as identified through a screening procedure, 4) currently taking HIV medication and 5) a patient receiving care at one of the study recruitment sites. Based on NIAAA's screening recommendations, every person living with HIV who reports to participating clinics will complete a short screening procedure. Clinical data of interest including alcohol dependency diagnoses and prescription use will be pulled from CDW via VINCI, CCR and HAVACS. These clinical indicators will be used to create a list of eligible patients with appointments in the coming month for screening. The list of eligible patients will be stored in the secure VINCI project folder and then downloaded to the secure local VA drive for use by study coordinators. The only two locations in which the list will be stored are within VINCI and on the secure local drive. After a list of patients has been created, the study coordinator will screen the patient EMR (CPRS/VISTA) for inclusion criteria.

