7. The research coordinator will check to see if the following inclusion criteria are met:
 - a. HIV-positive
 - b. 18 years or older
 - c. An at-risk drinker as identified by the alcohol screener
 - d. Currently taking HIV medication
 - e. A score less than 20 on the AUDIT questionnaire
 - i. Score is displayed on the final page of the questionnaire. If above 20, see step 9 below for further direction.
8. If patients are eligible, the research coordinator will provide them with a TRAC flyer and consent form
 - a. If the patient wants to enroll in the study, the coordinator will proceed with enrollment (see next section)
 - b. If the patient does not want to enroll today, they can take the TRAC flyer and consent form with them. If they want to enroll at a later date, they can call the VA coordinator.
 - c. They are eligible to begin the study if they enroll within 30 days. If they would like to join the study after that date, they will need to be re-screened.
9. If patients are ineligible because of a score of 20 or higher on the AUDIT questionnaire, a note will be made in their chart and a referral made to their clinical team for follow-up regarding concerning levels of alcohol use.
10. Screening activities will not collect any data to be used in the study.

Step 2: Patient Enrollment

1. The coordinator will go through the consent form and HIPAA form with the participant, discussing:
 - a. The overall purpose of the study
 - b. The time commitment of the study
 - c. Their expectations as a participant
 - d. The incentives they will receive
 - e. Any questions the participant has
2. Once the participant has demonstrated sufficient understanding of the consent and HIPAA forms, the research coordinator will obtain consent and a signature on the HIPAA form.
3. The research coordinator will assign the participant a numeric identifier and record it in the secure code key
 - a. The research coordinator will inform the participant that if they forget their study ID at any time, they can contact the researchers to learn what it is.
4. Only researchers will have access to this key, which will be kept in a password-protected file

5. The research coordinator will then check the randomization spreadsheet (pre-generated set of random numbers for each participant ID assigning them to the intervention or waitlist-control group)
 - a. If they are in the intervention group (Group 1):

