8. During Session 8, the interventionist will schedule the following appointments, contacting the patient one day before all subsequent tasks to remind them:
 - a. Post-intervention appointment at the VA to complete assessment and return equipment (1 week later)
 - b. Booster session (to be completed via phone 5 weeks later)
 - c. Questionnaire #3, to be completed 9 weeks later
 - d. Questionnaire #4, to be completed 17 weeks later
9. The final session at the VA (Week 8) will include the following tasks:

- a. Returning of mobile phones (if applicable) and breathalyzers
- b. Post-intervention assessment battery, completed using a laptop
- c. Reminder of all subsequent appointments/tasks for the study
10. At 12 weeks, the interventionist will contact the participants to complete a 30-minute intervention booster session via phone. This session will review the participant's drinking goals and provide a refresher on the different types of triggers and strategies to address them.
11. At 16 weeks, the interventionist will contact the participants and ask them to complete a follow-up assessment battery at home (on a computer, tablet, or mobile phone—no clinic visit will be required)
 - a. Participants will be given the option to come to the VA to complete the questionnaire if desired
 - b. If assessment is not done within a week, researchers will contact the participant to encourage participation and ensure that no adverse events had occurred
 - i. If patients cannot be reached, researchers will attempt to contact them three additional times (one day later, three days later, and one week later). If they cannot be contacted by the third attempt, they will be considered lost to follow-up and will not be contacted again.
12. At 24 weeks, the interventionist will contact the participants and ask them to complete an additional follow-up assessment battery at home (on a computer, tablet, or mobile phone)—no clinic visit will be required
 - a. Participants will be given the option to come to the VA to complete the questionnaire if desired
 - b. If assessment is not done within a week, researchers will contact the participant to encourage participation and ensure that no adverse events had occurred

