 - i. If patients cannot be reached, researchers will attempt to contact them three additional times (one day later, three days later, and one week later). If they cannot be contacted by the third attempt, they will be considered lost to follow-up and will not be contacted again.
13. After the participant completes the study, a retrospective chart review will be conducted to obtain viral load measurements (minimum of 2) from the participant during the time period beginning 3 months prior to their entry into the study and up to 6 months after their entry into the study.

3b. Waitlist-control group

1. After randomization and enrollment, the participant will complete the baseline assessment either at the time of enrollment, at home, or during a subsequent appointment within the next 30 days
2. The interventionist will call the participant after enrollment and do the following:
 - a. Introduce themselves to the patient
 - b. Describe the study timeline
 - c. Discuss follow-up contact times and encourage the participant to stay in contact
 - d. Remind participant of incentives they will receive for participating
 - e. Provide information about the baseline assessment (if the participant has not already completed it)
3. The interventionist will contact participants using their chosen method of communication after 4 weeks to maintain contact and ensure that no adverse events have occurred
4. At 7 weeks, the interventionist will contact participants to obtain their availability for the next week to schedule the first intervention content session based on the shared calendar
5. One day before the videoconferencing session, the researcher will contact the participant via the participant's chosen method of contact to remind them of their appointment
6. At 8 weeks, the patient will come into the clinic to begin the intervention.
7. The patient will be given a laptop to complete the initial assessment battery
8. If the participant is in need of a study phone, the VA coordinator will provide this phone, along with the breathalyzer, to the participant
9. The participant will begin the first intervention session, which will consist of the following content/tasks:
 - a. Introductions and orientation to the technology (smartphone and breathalyzer, stored at the clinic; tutorial handouts provided)

- b. Review of self-monitoring procedures and setting of “do not disturb” hours
 - c. Review of breathing awareness exercise

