In the event that identifying information is released to an unauthorized party, the serostatus of participants could be revealed to unwanted individuals. This could potentially cause harm, but is unlikely considering the careful plans in place regarding data management and protection. All possible measures will be taken to protect information provided through surveys, interviews, and intervention participation, and confidentiality will be respected. Following completion of data collection, responses will become anonymous as identifying information is permanently deleted. For these reasons, we estimate that this minimally-invasive project poses minimal risk.

STATISTICAL ANALYSIS PLAN

For the randomized controlled trial, data analytic methods will be focused on examining acceptability and feasibility, as well as effects on alcohol intake, HAART adherence, and HIV-related medical outcomes (CD4 count and viral load). Intervention adherence, daily monitoring adherence, and session acceptability will be described using descriptive statistics. Session attitudes will be assessed using several 5-point semantic differential attitudinal measures rating the session, including Boring/Interesting, Unpleasant/Pleasant, Bad/Good, Useless/Useful, and Negative/Positive. Scores on the session attitude semantic differential measures will be reverse-coded where required and averaged to form an overall attitude score, with “0” being “neutral.”

We will provide descriptive summaries for the outcome variables, including mean, median, and standard deviation for continuous variables and counts and percentages for categorical variables. We will summarize the outcome variables overall and across the intervention groups. In assessing the differences in alcohol use and medication adherence between the two groups during the 8-week intervention period, we will utilize the Kruskal–Walli’s test, a non-parametric statistical approach, to compare the distribution of outcome variables. The general linear model (ANOVA) will be used to estimate the difference between alcohol use and medication adherence among the groups, and the estimation of the effect size (Cohen’s D) at the end of the 8-week intervention period. While this study was not powered to detect significant differences, the goal of these analyses is to observe changes and effect sizes that may provide preliminary evidence of efficacy.

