To examine intervention effects as assessed through daily surveys, we will examine responses to the morning survey question asking if participants had consumed alcohol on the previous day (yes/no), whether or not they reported a positive breathalyzer reading (> 0.0), and if they had taken all of their HAART on the previous day (yes/no). Within the 8-week intervention period and using the daily data, we will assess the change in the proportion of participant's alcohol use, the proportion of positive breathalyzer readings, and the proportion of their medication use from the beginning of week 1 to the end of week 8 using McNemar's matched pair test. This test will allow us to address the interdependency in the repeated measurements. We will account for missing survey responses by considering two scenarios: First, assuming they were missing completely at random and remained missing, and second, that missing values were indicative of alcohol use/medication nonadherence and were thus filled in as drinking days/positive breathalyzers/nonadherent days (a conservative approach).

All participants will have received the intervention by the end of the 8 week (2-month) post-intervention period. To examine long-term intervention effects, participants from both the waitlist-control and intervention group will be combined into a single dataset. A generalized linear model (via SAS GENMOD PROCEDURE) and a multiple linear regression model will be fit to the change from baseline for each outcome measure. Change from baseline is the difference between the baseline value and values obtained at subsequent time points: 8 weeks (immediate post-intervention; T2 for intervention group and T3 for waitlist-control), and 16 weeks (2 months post-intervention; T3 for intervention group and T4 for waitlist-control) for each outcome measure. The rationale for fitting the change from baseline is that this model removes the effect of baseline differences that may exist from the model. All statistical hypothesis tests will be conducted using the standard 5% significance level. SAS Version 9.4 (TS1M1, SAS Institute, Cary, NC), will be used for all analyses.

References

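### The week-8 questionnaire, which carries the only randomised comparison, is tied to attending treatment and has no home option or follow-up of non-completers outside the COVID-19 deviation

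*Combined protocol and SAP*

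**What the plan says.** Section 5 (Collection and record keeping) has both groups completing the battery at baseline and weeks 8, 16 and 24. The between-arm analysis is in the second paragraph of the SAP: a Kruskal–Wallis comparison of alcohol use and medication adherence, and a linear model giving "the estimation of the effect size (Cohen’s D) at the end of the 8-week intervention period". The last paragraph of the SAP pools the arms for longer-term effects.

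Section 4, Step 3 sets out how the batteries are obtained:

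- **Intervention arm, week 8 (Step 3a, items 8–9).** "During Session 8, the interventionist will schedule the following appointments", the first of which is "Post-intervention appointment at the VA to complete assessment and return equipment (1 week later"). The battery is done at that visit on a laptop.
- **Waitlist arm, week 8 (Step 3b, items 4–9).** Staff make contact at week 7 to arrange Session 1. Then "At 8 weeks, the patient will come into the clinic to begin the intervention", with the battery on a laptop at that visit, before the session.
- **Later follow-ups (Step 3a, items 11–12; Step 3b, item 15).** Staff make contact at the calendar week and the battery can be done at home. "If assessment is not done within a week, researchers will contact the participant to encourage participation and ensure that no adverse events had occurred". Up to three further attempts follow for those not reached.
- **COVID-19 deviation.** While clinic visits are judged unsafe, all questionnaires move to remote completion, with paper if needed.

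**The concern.** A participant in the intervention arm who stops sessions at, say, week 4 does not reach the step that books the week-8 outcome. A waitlist participant who no longer wants the intervention has no separate occasion to give it. Both losses are related to engagement, but they are different events: leaving treatment in one arm, not starting it in the other. The people observed at week 8 may then no longer be comparable across arms.

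This matters because the SAP says that the study was not powered for significance and that its purpose is to observe changes and effect sizes. A distorted week-8 effect size is a distorted main efficacy output, and no later analysis can replace it.

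**Working it through.** **1. Which battery is booked in Session 8.** With weekly sessions, Session 8 falls at week 7. The offsets in Step 3a, item 8 (1, 5, 9 and 17 weeks) give weeks 8, 12, 16 and 24, which match items 9–12. In the waitlist arm Session 8 falls at week 15, and offsets of 1, 5 and 9 weeks give weeks 16, 20 and 24, which match Step 3b, items 13–15. So the visit booked in Session 8 is the week-8 battery in the intervention arm and the week-16 battery in the waitlist arm.

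**2. Whether other data could supply the comparison.** After week 8 the waitlist arm starts treatment and the SAP pools the arms. Daily monitoring runs only during each person's own intervention period (Section 5), so the waitlist arm has none before week 8. The SAP's rule for missing responses stands in the daily-data paragraph; none is given for a missing week-8 battery. Viral load comes from chart review and is not exposed in this way.

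**3. Handling of each battery, outside the COVID-19 deviation.**

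| Battery | Trigger described | Place | Home option | Repeat contact |
|---|---|---|---|---|
| Intervention, week 8 | Booked in Session 8 | VA, laptop | None described | None described |
| Waitlist, week 8 | Week-7 contact to book Session 1 | VA, laptop, at Session 1 visit | None described | None described |
| Intervention, weeks 16 and 24 | Listed in Session 8, plus staff contact at the calendar week | Home | Yes | Yes |
| Waitlist, week 16 | Booked in Session 8 | VA, laptop | None described | None described |
| Waitlist, week 24 | Listed in Session 8, plus staff contact at the calendar week | Home | Yes | Yes |

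Waitlist week 16 is that arm's immediate post-intervention value in the pooled model (SAP, last paragraph).

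**4. Possible bias.** Let p be the share of an arm lost at week 8 and g the gap, in SD of drinking, by which those lost exceed those observed. The observed mean of an arm is then too low by p × g. The apparent benefit of the intervention (arm 1) over waitlist (arm 0) is inflated by

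p1 × g1 − p0 × g0.

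The documents give neither p nor g. Assuming g = 0.8 in both arms:

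| p1 | p0 = 0 | p0 = 10% | p0 = p1 |
|---|---|---|---|
| 10% | 0.10 × 0.8 = 0.08 | 0.08 − 0.08 = 0 | 0 |
| 20% | 0.20 × 0.8 = 0.16 | 0.16 − 0.08 = 0.08 | 0 |
| 30% | 0.30 × 0.8 = 0.24 | 0.24 − 0.08 = 0.16 | 0 |

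If waitlist loss is the larger (p1 = 10%, p0 = 20%), the sign reverses: 0.08 − 0.16 = −0.08. With loss in the intervention arm only, of 10–40%, a gap of 0.5 SD gives 0.05–0.20 and a gap of 1.0 SD gives 0.10–0.40.

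**5. Scale.** Section 3 gives N = 50. The allocation is a "pre-generated set of random numbers for each participant ID assigning them to the intervention or waitlist-control group" with no ratio stated, so 25 per arm is an assumption; 20% loss would be 5 of 25 people. The standard error of the standardised difference is √(1/25 + 1/25) = 0.283, and the 95% half-width is about 0.57. With 20 per arm the half-width is 0.64. The loss of precision is modest; selective loss is the larger concern.

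**The case against.** The strongest reply is that the link to treatment is inferred from silence. Item 8 of Step 3a also lists Questionnaires #3 and #4, which staff later seek by calendar week, so being listed in Session 8 does not make an assessment conditional on that session. Section 5 says without condition that both groups complete the battery at 8 weeks. The questionnaire has its own payment, and intervention participants who stop still hold equipment due back at the VA. The waitlist arm is contacted at weeks 4 and 7, and both arms get a reminder the day before. This stands to the extent that nothing forbids staff from pursuing a week-8 battery. But Questionnaires #3 and #4 have a separate calendar step and a contact sequence, and the week-8 battery has neither. The week-7 waitlist contact serves to book Session 1.

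A reader might infer that the intervention-arm data come only from people who finished all eight sessions. The text does not say so: someone who missed earlier sessions but took part in Session 8 would be booked. A reader might also infer that remote completion is never possible. The COVID-19 deviation allows it, though conditionally and temporarily. Section 5 also describes the 8-week questionnaire as online, on a tablet or mobile phone. That names a device and not a home option, but it does not agree with the laptop-at-clinic steps and should be reconciled with them.

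Finally, a bias figure that counts loss in one arm only is one-sided. That is correct, and it is why the formula above has two terms.

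**Conclusion.** The point holds as a weakness in outcome collection. Outside the COVID-19 deviation, the written steps tie the week-8 battery to treatment attendance, differently in each arm, and describe no home option or retrieval for it. Waitlist week 16 shares the gap.

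The consequence is a risk of bias, not a demonstrated one. It is 0.08–0.24 SD towards benefit if 10–30% are lost from the intervention arm alone and the gap is 0.8 SD, and smaller, zero or reversed if waitlist loss is similar or larger. It is tempting to conclude that the effect size will be biased towards benefit. The documents do not support that, since they give no drop-out rate for either arm and no completer–drop-out gap.

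**What to change.** - Set the week-8, 16 and 24 questionnaire dates by calendar time from a stated origin (baseline or enrolment), and say that they are sought from every randomised participant whatever the number of sessions attended.
- Extend the existing home-completion option and contact sequence to week 8 in both arms and to waitlist week 16.
- Request the waitlist week-8 battery even if Session 1 is declined or delayed, keeping the existing order of battery before Session 1.
- Reconcile the device wording in Section 5 with the laptop steps in Step 3.

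The online battery and contact sequence already exist, so this is a change of wording. The cost is a few more staff contacts and some batteries completed at home rather than in clinic. It reduces selective loss but does not say how any remaining missing week-8 data are to be analysed.

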 - d. Scheduling follow-up intervention sessions for sessions 2-8, conducted via mobile phone.
 - e. A short post-session satisfaction survey, delivered via text message and completed immediately following the session.
10. The day after the first session, participants will begin self-monitoring their alcohol, medication use, and mental health
- a. They will be texted at two random times each day using an automated software to complete a breathalyzer reading and finish a survey
 - b. If participants do not respond to the request within 30 minutes by replying with “C” to confirm they completed the tasks, a text reminder will be sent, followed by another an hour later.
 - i. If the participant is in a situation where they are unable to complete the breathalyzer test, they will be able to respond to the text message and request a follow-up reminder two hours later.
 - c. If participants wish to go to sleep for the night and have not yet received their evening reminder, they can elect to complete a breathalyzer reading and survey before going to bed.
 - d. Self-monitoring will continue until the day of the final intervention session
 - e. Participants will be instructed to call the interventionist if they have any technical difficulties throughout the course of the study
11. Sessions 2-8 of the intervention will be conducted via phone call, with patients instructed to find a private room from which to speak with their counselor
- a. After each session, participants will complete a short post-session satisfaction survey, delivered via text message and completed immediately following the session
12. During Session 8, the interventionist will schedule the following appointments, contacting the patient one day before all subsequent tasks to remind them:
- a. Post-intervention appointment at the VA to complete assessment and return equipment (1 week later)
 - b. Booster session (to be completed via phone 5 weeks later)
 - c. Questionnaire #4, to be completed 9 weeks later
13. The final session at the VA (Week 16) will include the following content/tasks:
- a. Returning of mobile phones and breathalyzers
 - b. Post-intervention assessment battery, completed using a laptop
 - c. Reminder of all subsequent appointments/tasks for the study

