Participants in the proposed research will benefit primarily by receiving free alcohol reduction counseling, which has potential to not only reduce their alcohol use, but improve their HIV medication adherence and, in turn, their overall health. The self-monitoring aspect will also increase their own awareness of their behaviors and potentially improve their ability to recognize contextual predictors that encourage alcohol use or a lack of medication adherence. Finally, participants will receive financial compensation for their participation. All participants will receive these benefits with minimal effort, as the intervention requires few in-person visits, while the rest can be received via mobile phone.

For all participants, there is the potential risk of anxiety or discomfort when reporting opinions or receiving educational intervention content. The interviews and surveys will address sensitive information or information that may cause embarrassment, such as substance use behaviors and mental health status. Additionally, there is also the risk of loss of confidentiality, as identifying information will be collected in order to monitor participants' data throughout the course of the planned research, as well as to obtain their HIPAA authorization.

There are also inherent risks in using communication technologies for delivering a health intervention. The videoconferencing sessions of the intervention will occur over a HIPAA-compliant secure network, so they will pose no risk. However, any of the activities done using mobile phones, including intervention sessions and self-monitoring, are inherently less secure. Participants and study personnel will receive thorough training on how to secure their mobile phones to prevent any unauthorized access to data, and each phone will have the potential to be remotely wiped in case of theft or loss. The study coordinator will explain this issue carefully and get consent of understanding as part of the study protocol.

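### No scheduled adverse-event enquiry reaches a compliant participant during or after TRAC; explicit enquiry depends on arm and on late questionnaires

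*Combined protocol and SAP*

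**What the plan says.** Adverse events are mentioned at four points, all in Section 4 (Study Design), Step 3.

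- Step 3a (intervention), item 11b, week 16: "If assessment is not done within a week, researchers will contact the participant to encourage participation and ensure that no adverse events had occurred".
- Step 3a, item 12b, week 24: the same condition. It attaches to the contact at which staff "ask them to complete an additional follow-up assessment battery at home".
- Step 3b (waitlist), item 3: the interventionist contacts every participant "after 4 weeks to maintain contact and ensure that no adverse events have occurred". This is unconditional. TRAC starts later in this arm: "At 8 weeks, the patient will come into the clinic to begin the intervention".
- Step 3b, item 15b, week 24: the same late-questionnaire condition.

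Section 6 (Potential benefits/risks) accepts that "there is the potential risk of anxiety or discomfort when reporting opinions or receiving educational intervention content". It also names loss of confidentiality, including disclosure of HIV status, and concludes that the project poses minimal risk. The Statistical Analysis Plan names no adverse-event summary.

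**The concern.** Where adverse-event enquiry is scheduled, it follows the wrong variable. It is certain for untreated controls at week 4, and otherwise depends on a questionnaire being more than a week late. Neither condition relates to receiving the eight sessions, the self-monitoring or the booster.

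Two things are at stake. A participant who has a problem during TRAC but answers on time is not asked about it as an adverse event. And any adverse-event tally the trial produced would reflect who was asked rather than who was exposed, so a low count could not be offered as evidence for the minimal-risk statement. For a pilot meant to judge feasibility and acceptability, basic tolerability information is part of what a later trial would need.

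**Working it through.** The documents give no adverse-event rate and no calculation to reproduce. The check is a count of explicit enquiries for a participant who attends everything and returns every questionnaire on time.

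**Contacts examined**

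- Sessions 1-8: the session table and the scripted delivery described under Study Intervention list no adverse-event question.
- End-of-TRAC visit, intervention arm: "The final session at the VA (Week 8) will include the following tasks". Three tasks follow (equipment, assessment battery, reminders), none of them an adverse-event question.
- End-of-TRAC visit, waitlist arm: "The final session at the VA (Week 16) will include the following content/tasks". The same three kinds of task follow. Week 16 therefore carries no adverse-event trigger in this arm, not even a conditional one.
- Booster (week 12 or 20): "This session will review the participant's drinking goals and provide a refresher on the different types of triggers and strategies to address them". No adverse-event question.
- Batteries, daily surveys and post-session surveys (Section 5, Collection and record keeping): no adverse-event item is listed.
- COVID-19 deviation section: adds none.

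**Explicit enquiries, fully compliant participant**

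| Period | Intervention | Waitlist |
|---|---|---|
| Weeks 0-8 (randomized comparison) | 0 | 1 (week 4, before TRAC) |
| Weeks 8-24 | 0 | 0 |
| During or after TRAC | 0 | 0 |
| Conditional triggers if late | 2 (weeks 16, 24) | 1 (week 24) |

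The imbalance runs towards the waitlist arm in weeks 0-8 and, among late responders, towards the intervention arm afterwards.

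**What compliant participants are asked** (Section 5)

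- Twice daily during TRAC: anxiety and depression.
- After each of the eight sessions: ratings, attitudes, therapeutic alliance and an open-ended reaction.
- At baseline and weeks 8, 16 and 24, in both arms: anxiety, depression, stress and post-traumatic stress symptoms.

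No sentence links these answers to review for harm, to a contact, or to an adverse-event record. No listed item asks about loss of confidentiality.

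**Illustration of scale (rates assumed)**

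If n people are asked and a share p has an event, the chance that at least one affected person is found is 1 − (1 − p)^n. Assume that 10%, 20% or 30% of the 50 are late (5, 10 or 15 people), that all of them are reached, and that lateness is unrelated to events.

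| Assumed p | All 50 asked | 5 asked | 10 asked | 15 asked |
|---|---|---|---|---|
| 2% | 63.6% | 9.6% | 18.3% | 26.1% |
| 5% | 92.3% | 22.6% | 40.1% | 53.7% |
| 10% | 99.5% | 41.0% | 65.1% | 79.4% |

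For example, at p = 5%: 1 − 0.95^50 = 0.923 and 1 − 0.95^10 = 0.401. The table ignores spontaneous reports and the mental-health items, so it describes explicit enquiry only.

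**The case against.** The strongest reply is that participants on TRAC are hardly out of sight. They speak to a counselor weekly, with time set aside for questions. They report anxiety and depression twice a day, and anxiety is a harm that Section 6 itself names. They comment freely after each session and complete mental-health batteries on the same calendar in both arms. On this view the explicit contacts are there for people otherwise out of touch: waitlist participants and non-responders. The trial is a 50-person behavioural pilot, and the SAP proposes no comparison of harms.

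Much of this stands, and it rules out some stronger readings:

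- A reader might infer that compliant participants are never asked about anything that could be a harm. The Section 5 lists contradict that.
- A reader might infer that a planned harm comparison is biased. The SAP plans none.
- A reader might take the week-16 trigger to apply to both arms. It applies to the intervention arm only.

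What the reply does not do is close the gap. Session discussion is described in terms of drinking, and the only stated reason for a participant to call in is technical difficulty. Daily and post-session surveys run only during TRAC, so in weeks 0-8 they have no control counterpart. Section 5 calls its listed variables outcomes, so the SAP's general descriptive summaries could be read as including the mental-health scores, but nothing presents them as harms or turns an individual answer into a recorded event. Spontaneous reporting is possible but unsystematic.

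**Conclusion.** The gap is real but narrow. During or after TRAC, a compliant participant in either arm receives 0 scheduled adverse-event enquiries. In the randomized weeks 0-8 the count is 0 (TRAC) against 1 (waitlist). The anxiety, depression and stress items and the open reactions are collected, but the text does not connect them to adverse-event recording, and loss of confidentiality is not asked about. Adverse-event counts gathered this way would depend on arm and lateness rather than exposure, and could not support the minimal-risk statement.

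This is worth correcting, but it does not undermine any analysis the SAP proposes. A reader might want to express the flaw through exact zero-event limits: 1 − 0.025^(1/50) = 7.1% for 50 people, or 1 − 0.025^(1/25) = 13.7% for 25 per arm. Those are generic limits that assume full retention and, for the second, 1:1 allocation, which the documents do not state. They do not measure this gap.

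The conclusion rests on the step-by-step procedures, data lists and SAP. The opening part of the document and the consent pages were not available, so reporting instructions there cannot be excluded.

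**What to change.** Ask one identical adverse-event question of every participant, whether or not the questionnaire is on time:

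- in the existing batteries at weeks 8, 16 and 24, in both arms;
- at week 4 in both arms, using the existing waitlist contact and the intervention session held that week;
- at the mid-treatment session of the waitlist arm, about week 12.

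Keep the late-responder contact as a back-up. Record each event with its date, and state who reviews the answers. Say whether the anxiety, depression and open-reaction responses feed into that record, and word the question so that it covers loss of confidentiality.

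Add one descriptive SAP table: events by arm for weeks 0-8, and events during and after TRAC for all participants.

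A compliant participant would then be asked twice in weeks 0-8 in each arm (weeks 4 and 8). Counted from the start of TRAC, both arms would be asked at about 4, 8 and 16 weeks: weeks 4, 8 and 16 for intervention; weeks 12, 16 and 24 less the 8-week wait for waitlist. The intervention arm would have one further enquiry at week 24.

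The cost is one survey item, one line in the week-4 contact and in the mid-treatment session script, one table, a few minutes of participant time, and some staff time to review answers. No visit is added.
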